CVN766 45 mg, CVN766 125 mg, CVN766 250 mg.

Figure 14.2.3.6.1 Plasma t1/2z versus dose for CVN766 SAD (Log Scale) (Pharmacokinetic Population)

[figure not shown]
Programing Note:
Same as Figure 14.2.3.1.1
Source Listing: 16.2.6.1.1
Add following treatment;
CVN766 5 mg, CVN766 15 mg, CVN766 45 mg(Fasted), CVN766 125 mg, CVN766 250 mg.

Figure 14.2.3.6.2 Plasma t1/2z versus dose for CVN766 MAD (Log Scale) (Pharmacokinetic Population)

Programing Note:
Same as Figure 14.2.3.1.1
Source Listing: 16.2.6.1.2
Add following treatment;
CVN766 45 mg, CVN766 125 mg, CVN766 250 mg.

Figure 14.2.4.1.1 Dose-normalized Cmax versus dose for CVN766 SAD (Pharmacokinetic Population)

Pharmacokinetic parameter: Cmax

Source Listing: 16.2.6.1.1

O Original values
—●— Geometric Means

Programming Note:

The x-axis represents dose from 5 to 250 mg.
The y-axis will represent the dose normalized Cmax.

Programming Note:

Add following treatment;
CVN766 5 mg, CVN766 15 mg, CVN766 45 mg (Fasted), CVN766 125 mg, CVN766 250 mg.

Figure 14.2.4.1.2 Dose-normalized C_{max,ss} versus dose for CVN766 MAD (Pharmacokinetic Population)

Programing Note:
Same as Figure 14.2.4.1.1
Source Listing: 16.2.6.1.2
Add following treatment;
CVN766 45 mg, CVN766 125 mg, CVN766 250 mg.

Figure 14.2.4.2.1 Dose-normalized AUC_{inf} versus dose for CVN766 SAD (Pharmacokinetic Population)

Programing Note:
Same as Figure 14.2.4.1.1
Source Listing: 16.2.6.1.1
Add following treatment;
CVN766 5 mg, CVN766 15 mg, CVN766 45 mg (Fasted), CVN766 125 mg, CVN766 250 mg.

Figure 14.2.4.3.1 Dose-normalized AUC₂₄ versus dose for CVN766 SAD (Pharmacokinetic Population)

Programing Note:
Same as Figure 14.2.4.1.1
Source Listing: 16.2.6.1.1
Add following treatment;
CVN766 5 mg, CVN766 15 mg, CVN766 45 mg (Fasted), CVN766 125 mg, CVN766 250 mg.

Figure 14.2.4.3.2 Dose-normalized AUC₂₄ versus dose for CVN766 MAD (Pharmacokinetic Population)

Programing Note:
Same as Figure 14.2.4.1.1
Source Listing: 16.2.6.1.2
Add following treatment;
CVN766 45 mg, CVN766 125 mg, CVN766 250 mg.

Figure 14.2.4.4.1 Dose-normalized AUC_t versus dose for CVN766 SAD (Pharmacokinetic Population)

Programing Note:
Same as Figure 14.2.4.1.1
Source Listing: 16.2.6.1.1
Add following treatment;
CVN766 5 mg, CVN766 15 mg, CVN766 45 mg (Fasted), CVN766 125 mg, CVN766 250 mg.

Figure 14.2.4.4.2 Dose-normalized AUCt versus dose for CVN766 MAD (Pharmacokinetic Population)

Programing Note:
Same as Figure 14.2.4.1.1
Source Listing: 16.2.6.1.2

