2.1.1 Part 1: SAD is the single-dose regimen and Fasted- Fed Crossover

Approximately 40 healthy male or female subjects will be enrolled in 1 of 5 single-dose cohorts (designated as S1 through S5, respectively) in an ascending fashion. An optional Cohort 3a may be added in parallel to SC3 for additional safety and tolerability evaluation. Cohort S3a dose level will be consistent with Cohort S3 (45 mg planned) in a fasted condition only and without lumbar puncture, aligned with other SAD cohorts. Each cohort will consist of 8 subjects randomized to CVN766 or placebo, whereby 6 subjects will receive a single oral dose of CVN766 suspension, and 2 subjects will receive a matching placebo suspension under overnight fasted conditions. Sentinel dosing (1 subject to receive CVN766 and 1 subject to receive placebo) will be used in each cohort to ensure adequate safety and tolerability evaluation prior to administering CVN766 or placebo to the remainder of the subjects within the cohort. The planned dose levels will be 5, 15, 45, 125, and 250 mg CVN766. Each following dose level may be higher, lower, or remain the same as the preceding cohort. Additional cohort(s) may be added if deemed necessary by the SRG to fully characterize the safety and tolerability of CVN766. To assess the effect of food on CVN766 bioavailability in suspension formulation, the single-dose administration will be repeated in a single cohort (S3) after ingestion of a standardized high-fat, high-calorie meal. Once the safety of the S3 cohort dose level has been assessed, the S3 cohort subjects will return to the clinic (no sooner than 14 days after their prior dose, or at least 4 half-lives, has lapsed based on preliminary PK data, whichever is longer). They will receive the same dose as before, administered after ingesting a standardized breakfast. Subjects will finish at least approximately 85% of their breakfast within 30 minutes and receive an investigational product 30 minutes (\pm 5 minutes) after beginning the meal. Sentinel dosing will not be required for subjects returning to the clinic for the fed regimen. If the CVN766 PK parameters in the fasted S3 cohort reveal poor absorption with inconclusive results, the fed cohort will be deferred until a higher dose level.

[figure not shown]
On Day 1, subjects will undergo safety monitoring and PK sampling from blood plasma through 72 hours post-dose and, for cohort S3 (fasted) only, from CSF via lumbar puncture at 3 hours post-dose

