2.1.2 Part 2 MAD is a Multiple-Dose Regimen

Approximately 24 healthy male and female subjects aged 18 to 55 will be enrolled in 1 of the 3 multiple-dose cohorts (designated as M1 through M3, respectively) in an ascending fashion. The dose levels planned to be studied in the multiple-dose regimen are 45, 125, and 250 mg CVN766 for multiple-dose cohorts M1 through M3, respectively. Each multiple-dose cohort will consist of 8 subjects randomized to CVN766 or placebo, whereby 6 subjects will receive a daily oral dose of CVN766, and 2 subjects will receive matching placebo for 7 days. Dosing will be administered in the fasting state; the SRG can change this if exposure is higher in the fed state. The planned dosing duration for the multiple-dose cohorts is 7 days. However, the duration may be increased to \leq 14 days if preliminary PK data suggest steady-state will not be achieved within 6 days of daily dosing.

On Day 1 subjects, will undergo safety monitoring and PK sampling from blood plasma through 24 hours post-dose and on Day 7, will undergo safety monitoring and PK sampling from blood plasma through 72 hours post-dose. Additionally, PK samples will be collected on Days 3, 4, 5 and 6 prior to the next planned dose. For cohort M1, on day 7 only, subjects will undergo PK sampling from CSF via lumbar puncture at 3 hours post dose and PK sampling from urine over 24 h on Day 1 and Day 7. CSF samples may also be taken from M2 and M3 cohorts at the SRG's discretion.

Figure 1: Study Design

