3.3 Inferential Analyses

Descriptive statistics will be used to summarize the safety and PK data. No formal hypothesis testing is planned.

All analyses (unless otherwise specified) will be performed at a two-sided 10% level of significance.

- Dose Proportionality

Dose proportionality will be evaluated for C_{max} , AUC_{inf} , AUC_t , AUC_{24} (SAD) and steady state parameters AUC_{tau} and $C_{max,ss}$ (MAD). Data will be presented graphically and a statistical analysis using the power model will be conducted. The analysis will be divided into days:

SAD: C_{max} , AUC_{24} , AUC_t , AUC_{inf}

MAD Day 1: C_{max} , AUC_{24}

MAD Day 7: $C_{max,ss}$, AUC_{tau} .

The model will include the \log_e -transformed CVN766 dose level as an independent variable. This model will be used to investigate the null hypothesis ($H_0: \beta=1$). Dose proportionality will be rejected ($H_1: \beta$ not equal 1) if the 90% CI of the estimated slope falls outside the critical interval.

The power model will have the form:

$$Y = a*(dose)^b$$

where Y is the PK parameter, and a and b are the coefficient and exponent, respectively, of the power equation.

By taking the natural logarithm (ln), the power model can be analyzed using linear regression and has the form:

$$\ln(Y) = \ln(a)+b*\ln(dose) + error = \alpha + \beta*\ln(dose) + error,$$

where α is the intercept, and β is the slope, and $\ln(dose)$ is based on the dose size for each subject. Estimates of slope and intercept along with their 90% confidence intervals will be reported. A minimum of 3 values per dose must be available for a given parameter to estimate dose proportionality using the power model. For dose proportionality, the slope of the regression line (b) = 1 and for dose independence $b = 0$.

Apparent dose linearity and proportionality of PK Parameters will be assessed graphically as well. The scatter plots and power model regression line will be plotted together with the natural log-transformed PK parameters as the values on the y-axis, and the natural log-transformed dose level as the values on the x-axis. Regression/scatter plot for SAD and MAD in the log-log scale for the Hummel power analysis will be performed by day.

- Food Effect

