10.5 Pharmacokinetic Parameters

Part 1 – Single Ascending Doses

The following pharmacokinetic parameters will, where possible, be determined from the plasma concentrations and CSF of analyte using non-compartmental methods via Phoenix WinNonlin Version 8.3 or higher.

Part 1 – Single Ascending Dose

Parameter	Definition
C_{max}	Observed maximum CVN766 concentration which is directly determined from the plasma concentration time profiles
T_{max}	Time to observed maximum observed CVN766 concentration. If the same C_{max} concentration occurs at different time points, T_{max} is assigned to the first occurrence of C_{max} .
T_{last}	Time to last observed CVN766 concentration.
AUC_{24}	The area under the plasma CVN766 concentration-time curve, from time 0 (time of dosing) to 24 hours, calculated by linear trapezoidal/ linear interpolation method
AUC_t	Area under the drug concentration-time curve, from time 0 (time of dosing) to the last measurable concentration using linear trapezoidal/ linear interpolation method
AUC_{inf}	The area under the plasma CVN766 concentration-time curve from time 0 (time of dosing) extrapolated to infinity. AUC_{inf} is calculated as the sum of AUC_t plus the ratio of the last measurable plasma concentration (C_{last}) to the elimination rate constant (λ_z), calculated by linear trapezoidal/ linear interpolation method.
$AUC_{\%extrap}$	The percentage of the AUC that has been extrapolated beyond the last observed data point, using the following formula, calculated by linear trapezoidal/ linear interpolation method $AUC_{\%extrap} = (AUC_{inf} - AUC_t) / (AUC_{inf}) * 100$
λ_z	Apparent terminal elimination rate constant calculated by linear regression of the terminal linear portion of the log concentration vs. time curve.
$t_{1/2}$	Apparent plasma terminal half-life calculated as $\ln(2) / \lambda_z$
CL/F	Apparent total plasma clearance, using the following formula $Dose / AUC_{inf}$
V_z/F	Apparent volume of distribution based on the terminal phase, reported to 3 significant figures and calculated as: $Dose / (\lambda_z \times AUC_{inf})$.
CSF:Plasma ratio	Ratio of the CVN766 concentration in CSF vs. the CVN766 concentration in plasma at 3h post dose.
DN_ C_{max}	Dose-normalized $C_{max} = C_{max} / dose$
DN_ AUC_{24hr}	Dose-normalized $AUC_{24hr} = AUC_{24hr} / dose$
DN_ AUC_t	Dose-normalized $AUC_t = AUC_t / dose$

DN_AUC _{inf}	Dose-normalized AUC _{inf} = AUC _{inf} /dose
-----------------------	---

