Figure 14.2.4.1.1 Dose-normalized Cmax versus dose for CVN766 SAD (Pharmacokinetic Population) 124

Figure 14.2.4.1.2 Dose-normalized Cmax,ss versus dose for CVN766 MAD (Pharmacokinetic Population) 125

Figure 14.2.4.2.1 Dose-normalized AUCinf versus dose for CVN766 SAD (Pharmacokinetic Population) 125

Figure 14.2.4.3.1 Dose-normalized AUC24 versus dose for CVN766 SAD (Pharmacokinetic Population) 125

Figure 14.2.4.3.2 Dose-normalized AUC24 versus dose for CVN766 MAD (Pharmacokinetic Population) 125

Figure 14.2.4.4.1 Dose-normalized AUCt versus dose for CVN766 SAD (Pharmacokinetic Population) 125

Figure 14.2.4.4.2 Dose-normalized AUCt versus dose for CVN766 MAD (Pharmacokinetic Population) 126

Figure 14.2.4.5.1 Dose-normalized AUCtau versus dose for CVN766 MAD (Pharmacokinetic Population) 126

Figure 14.2.4.6.1 Dose-normalized t1/2z versus dose for CVN766 SAD (Pharmacokinetic Population) 126

Figure 14.2.4.6.2 Dose-normalized t1/2z versus dose for CVN766 MAD (Pharmacokinetic Population) 126

GENERAL COMMENTS

- Where a count is 0, the percentage will not be shown (e.g. 0(0.0%) will be displayed as 0)
- Unless otherwise states, parameters will be listed in alphabetical order.
- The minimum and maximum values will be presented to the same number of decimal places as recorded in the electronic Case Report Form (eCRF)
- Mean, SD, and Median will be presented to one more decimal place than the raw data
- Percentages will be rounded to one decimal place, with the denominator being the number of subjects in the relevant population with non-missing data, unless otherwise specified
- Change from Baseline:
Change from Baseline will be calculated as:
$$\text{Change from Baseline} = \text{post baseline value} - \text{baseline value}$$
- Percentage change from Baseline
% Change from Baseline will be calculated as:
$$\% \text{ Change from Baseline} = (\text{post baseline value} - \text{baseline value}) / \text{baseline value} \times 100$$
- Unscheduled visits will be excluded from summary tables but included in all by-participant listings.
- **Names and order of Treatment Groups for Table Summaries**
 - Group 1 = SAD
 - Group 2 = MAD
- **Names and order of Treatment Groups for Tables/Listings**
- SAD:
 - CVN766 5 mg
 - CVN766 15 mg
 - CVN766 45 mg (Fasted)
 - CVN766 45 mg (Fed)
 - CVN766 125 mg
 - CVN766 250 mg
 - Overall CVN766 (Table only)
 - Overall Placebo (Table only)
 - Placebo (Fed; Table only)
 - Overall (Table only)

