Source Listing: 16.2.6.4.1
Add following treatment;
CVN766 45 mg
Include Visit = Day 1 and Day 7

Table 14.2.6.1 Statistical Analysis of Dose Proportionality for CVN766 SAD (Pharmacokinetic Population)

Analyte: xxxx

Parameter	n	Intercept Estimate	Slope	
			Estimate	90% CI
AUC _{inf}	xx	x.xx	xxx.xx	(x.xx, x.xx)
AUC _t	xx	x.xx	xxx.xx	(x.xx, x.xx)
AUC ₂₄	xx	x.xx	xxx.xx	(x.xx, x.xx)
C _{max}	xx	x.xx	xxx.xx	(x.xx, x.xx)

Source Listing: 16.2.6.3.1
 CI = Confidence Interval.
 Power Model: Ln(PK)=intercept + Ln(dose)

Dose proportionality can generally be concluded if the 90% CIs around the slope estimate (i.e., β1) include the value of 1 and is supported by the descriptive and graphical interpretation.

Programming Note:
 Include only the following cohorts;
 CVN766 5 mg, CVN766 15 mg, CVN766 45 mg(Fasted), CVN766 125 mg, CVN766 250 mg.

Table 14.2.6.2 Statistical Analysis of Dose Proportionality for CVN766 MAD (Pharmacokinetic Population)

Analyte: xxx
 Day 1

Parameter	n	Intercept Estimate	Slope	
			Estimate	90% CI
AUC ₂₄	xx	x.xx	xxx.xx	(x.xx, x.xx)
C _{max}	xx	x.xx	xxx.xx	(x.xx, x.xx)

Source Listing: 16.2.6.3.2
 CI = Confidence Interval.
 Power Model: Ln(PK)=intercept + Ln(dose)

Analyte: xxx
 Day 7

Parameter	n	Intercept Estimate	Slope	
			Estimate	90% CI
AUC _{tau}	xx	x.xx	xxx.xx	(x.xx, x.xx)
C _{max,ss}	xx	x.xx	xxx.xx	(x.xx, x.xx)

Source Listing: 16.2.6.3.2
 CI = Confidence Interval.
 Power Model: Ln(PK)=intercept + Ln(dose)

Dose proportionality can generally be concluded if the 90% CIs around the slope estimate (i.e., β_1) include the value of 1 and is supported by the descriptive and graphical interpretation.

Table 14.2.7.1 Food Effect Assessment of Plasma CVN766 Pharmacokinetic Parameters SAD(Pharmacokinetic Population)

Analyte:xxxx

Parameter (Unit)/ Statistics	CVN766 45 mg Fasted (N=xx)	CVN766 45 mg Fed (N=xx)
AUC _t (Unit)		
n	xx.xx	xx.xx
Geometric LS Mean (90% CI)	xx.xx (xx.xx, xx.xx)	xx.xx (xx.xx, xx.xx)
Ratio of Geometric LS Means (Fed/Fasting)		xx.xx
90% CI for Ratio of Geometric LS Means (Fed/Fasting)		(xx.xx, xx.xx)
AUC _{inf} (Unit)		
n	xx.xx	xx.xx
Geometric LS Mean	xx.xx	xx.xx
Ratio of Geometric LS Means (Fed/Fasting)		xx.xx
90% CI for Ratio of Geometric LS Means (Fed/Fasting)		(xx.xx, xx.xx)
AUC ₂₄ (Unit)		
n	xx.xx	xx.xx
LS Mean (SE)	xx.xx (xx.xxx)	xx.xx (xx.xxx)
Geometric LS Mean (90% CI)	xx.xx (xx.xx, xx.xx)	xx.xx (xx.xx, xx.xx)
Ratio of Geometric LS Means (Fed/Fasting)		xx.xx
C _{max} (Unit)		
n	xx.xx	xx.xx

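### The planned figures of dose-normalized half-life against dose would show a 1/dose decline even if half-life did not change with dose

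*SAP*

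**What the plan says.** Section 16 (Figures) and the contents list of the mock shells both plan two figures of this kind: "Figure 14.2.4.6.1 Dose-normalized t1/2z versus dose for CVN766 SAD (Pharmacokinetic Population") and "Figure 14.2.4.6.2 Dose-normalized t1/2z versus dose for CVN766 MAD (Pharmacokinetic Population").

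They close a series, 14.2.4.x, whose other members plot dose-normalized peak concentration and AUCs. In the shell for the first of these, Figure 14.2.4.1.1, the x-axis is dose from 5 to 250 mg, and on the other axis: "The y-axis will represent the dose normalized Cmax". The later shells shown in the series refer back to that one.

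Section 10.5 defines each dose-normalized parameter as the parameter divided by dose. The definitions cover Cmax, AUC24, AUCt and AUCinf in SAD, and Cmax,ss and the corresponding AUCs in MAD. Half-life has no such definition.

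Half-life against dose is also planned without normalization, on a log scale, as Figures 14.2.3.6.1 (SAD) and 14.2.3.6.2 (MAD). Section 2.3 names half-life as a secondary endpoint for both single and multiple dosing.

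**The concern.** Dividing by dose makes sense for a quantity that is expected to grow with dose. Cmax and AUC do so under linear kinetics, and a flat dose-normalized plot then signals proportionality. Half-life is expected to stay the same across doses under linear kinetics. Dividing it by dose builds in a decline that says nothing about the drug.

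The visual code is thus reversed within one figure series. In the neighbouring plots flat means linear kinetics. In these two, linear kinetics looks like a steep fall, and a flat plot would need a half-life that rises in proportion to dose. Someone who reads the series uniformly could report a dose trend in half-life that does not exist. The figures would also plot a variable that the SAP does not define in section 10.5 and does not carry in its parameter summary or listing shells.

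**Working it through.** The SAP gives no figure to reproduce here, so the check is algebra on its planned doses.

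**Inputs**
- SAD doses, section 2.1.1: "The planned dose levels will be 5, 15, 45, 125, and 250 mg CVN766".
- MAD doses, section 2.1.2: "45, 125, and 250 mg CVN766 for multiple-dose cohorts M1 through M3".
- Six active subjects per cohort, section 2.5.
- Normalization: division by dose, from section 10.5 and the shell of Figure 14.2.4.1.1.
- True half-life: not given. A constant 12 h is assumed, with 6 h and 24 h as a range.

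**Step 1: size of the built-in decline.** If half-life equals c at every dose d, the plotted value is c/d. The ratio of the lowest-dose to the highest-dose value is (maximum dose)/(minimum dose), and c cancels.
- SAD: 250/5 = 50-fold, a fall of 1 - 5/250 = 98%.
- MAD: 250/45 = 5.56-fold, a fall of 1 - 45/250 = 82%.

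**Step 2: plotted values (h/mg).**

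| Constant half-life | 5 mg | 15 mg | 45 mg | 125 mg | 250 mg |
|---|---|---|---|---|---|
| 6 h | 1.2 | 0.4 | 0.133 | 0.048 | 0.024 |
| 12 h | 2.4 | 0.8 | 0.267 | 0.096 | 0.048 |
| 24 h | 4.8 | 1.6 | 0.533 | 0.192 | 0.096 |

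The MAD figure would show the last three columns.

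**Step 3: slope.** Since ln(half-life/dose) = ln(half-life) - ln(dose), a log-log slope of b for half-life becomes b - 1 after division. Dose independence (b = 0) appears as -1. A flat plot requires b = 1, that is, a half-life 50 times longer at 250 mg than at 5 mg in SAD, or 5.56 times longer than at 45 mg in MAD.

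**Step 4: a real change can be hidden.** The 14.2.4.x titles do not carry the log-scale label that section 16 gives to the 14.2.3.x dose plots. If the SAD axis is linear and half-life doubled from 12 h to 24 h at 250 mg only, that point would move from 0.048 to 0.096 h/mg. The shift of 0.048 is 0.048/2.4 = 2% of the height at 5 mg.

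**Step 5: check with scatter.** Data were simulated with six active subjects per dose, a constant 12 h half-life, assumed log-normal CVs of 20%, 30% and 50%, and 5,000 runs per setting. The SAP's power-model regression was fitted with a 90% CI.
- Undivided half-life: mean slopes between -0.001 and 0.004. The CI included 0 in 89.3% to 90.9% of runs.
- Half-life divided by dose: mean slopes between -1.001 and -0.996. The CI included 0 in none of the runs in any setting.

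The SAP does not plan this regression for half-life. The simulation shows only that ordinary between-subject scatter would not mask the artefact.

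**Step 6: the SAP's other uses of half-life.** The sex comparison in section 3.3 is introduced as an analysis of dose-normalized parameters. It writes Cmax and the AUCs over dose but leaves half-life undivided. The same holds in section 10.7 and in the shells of Tables 14.2.8.1 and 14.2.8.2. Only the titles of the two figures pair half-life with dose normalization of its own.

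**The case against.** A reader might infer that these plots mislead the graphical assessment behind the dose-proportionality conclusion. The footnote to Tables 14.2.6.1 and 14.2.6.2 invites this, because it allows proportionality to be concluded where the 90% CIs for the slope "include the value of 1 and is supported by the descriptive and graphical interpretation". The SAP does not support that inference. Sections 3.3 and 10.7 list the parameters assessed for proportionality, all of them peak concentrations or AUCs, and the two tables have rows for those alone. The graphs that section 3.3 describes are log-log scatter plots with the fitted power-model line, which is the 14.2.3.x series. Nothing makes a half-life plot an input to the Cmax or AUC conclusions.

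The correct display is also already planned. Figures 14.2.3.6.1 and 14.2.3.6.2 show half-life undivided, and Tables 14.2.4.1 and 14.2.4.2 summarize it by dose. This stands, and it limits the harm.

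The titles may be a copying slip. The SAP uses the dose-normalized label loosely elsewhere: the title of Table 14.2.8.1 applies it to a table that also holds undivided half-life and Tmax. The individual shells for 14.2.4.6.1 and 14.2.4.6.2 are not visible, so the calculation is not confirmed. This stands as a caveat. It is the less likely reading, because two separate lists name both the parameter and its normalization, and the series shell plots normalized values.

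It would also go too far to say that the figures contradict the rest of the plan. No text forbids normalizing half-life. What the SAP lacks is a definition of the plotted variable.

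**Conclusion.** The point holds as a defect in two descriptive figures. If dose-normalized means divided by dose, as it does in every definition in section 10.5, a constant half-life would be shown as a 50-fold decline in SAD and a 5.56-fold decline in MAD, with log-log slope -1. These ratios rest on the planned doses, which section 2.1.1 allows to change in SAD. They do not depend on the assumed half-life. The display would be an artefact in a named secondary endpoint and would use an undefined variable.

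The reach is small. No estimate, confidence interval or dose-proportionality decision in the SAP depends on these figures, and a sound plot of the same endpoint is already planned.

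**What to change.** Delete Figures 14.2.4.6.1 and 14.2.4.6.2 from section 16 and from the mock shells, or plot half-life undivided under a corrected title. Rely on Figures 14.2.3.6.1 and 14.2.3.6.2 for half-life against dose.

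Add one sentence on how to read the retained figures. Their shells follow the Cmax shell, which draws a power-model curve, so a reader may look for a slope of 1. Section 3.3 already supplies both references: "For dose proportionality, the slope of the regression line (b) = 1 and for dose independence" b = 0. The sentence need only say that half-life is read against b = 0. No new test or formal criterion is required.

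The cost is two list entries, two shells and one line of text. Deletion saves programming, and undivided half-life remains both plotted and tabulated.
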